5. APPROACH –RESEARCH METHODS

A. STUDY DESIGN

Two - Arm, Randomized, Clinical trial (See Figure 1)

This proposal is designed to compare children and adolescents with newly diagnosed T1DM using a fixed insulin dose for fixed carbohydrate mealtime regimen (FIXED group) to children and adolescents with newly diagnosed T1DM using an ICR with variable carbohydrate intake (ICR group) mealtime regimen and determine:

1) Specific Aim 1

Determine the feasibility for a subsequent clinical trial involving rapid acting insulin dosing for a fixed dose for fixed carbohydrates (FIXED group) vs ICR with variable carbohydrate intake (ICR group) in order to determine the capacity for recruitment, caregiver consent to random assignment and completion of study measures, average session attendance, caregiver treatment adherence, and post-treatment satisfaction.

2) Specific Aims 2

- a) Determine if the caregivers of diabetics using a fixed insulin for fixed carbohydrate regimen (FIXED group) experience less anxiety than the caregivers of those using an ICR with variable carbohydrate intake regimen (ICR group) at 1- and 4-months post-randomization.
- b) Determine if diabetics utilizing a fixed insulin for fixed carbohydrate regimen (FIXED group) have decreased glycemic variability (GV) than those using an ICR with variable carbohydrate intake regimen (ICR group) at 1- and 4-months post-randomization.

We hypothesize that we will recruit and consent enough patients in order to perform a future, larger trial where caregivers of children and adolescents with newly diagnosed T1DM using a fixed insulin for fixed carbohydrate mealtime regimen (FIXED group) will experience less anxiety and their diabetic children will experience less GV than children and adolescents with newly diagnosed T1DM who use an ICR with variable carbohydrate intake at mealtime (ICR group). If this proves to be true, less anxiety may encourage more compliance and better glycemic control.

[figure not shown]

Figure 1: Study design and hypothesis.

3) Methods

a) Recruitment & Consent

Subjects with newly diagnosed T1DM will be evaluated by authorized study personnel under a HIPAA waiver to determine potential eligibility. The subjects will be contacted by the research study team while in the hospital during his or her initial diagnosis to explore his/her interest in the study and to confirm eligibility. The informed consent/assent documents will be signed at the time of the initial contact.

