The primary goal of this study is to determine the feasibility of a subsequent clinical trial of rapid acting insulin dosing for fixed carbohydrates (FIXED group) vs ICR with variable carbohydrate intake (ICR group). In doing so, we will examine our ability to recruit and consent patients (>70% consent rate), study retention (>90% retention), completion of study visits (average session attendance \geq 90%), study measures (\geq 90% measure completion), caregiver treatment adherence, and post-treatment satisfaction (\geq 90%),

2) Secondary Outcomes Measures

Secondary outcome measures will include caregiver anxiety and glycemic variability. Each of these measures are described below.

One secondary outcome measure is caregiver anxiety. This will be assessed by a parental stress scale [17]. The caregiver will fill out the questionnaire at initial enrollment (prior to hospital discharge) and at each clinic follow-up throughout the study. We will use the Spanish adaptation of parental stress scale (PSS) [18] for Spanish population if necessary.

We clarify in the survey that the questions are to be answered in terms of how the caregiver-child relationship exists since the diagnosis of diabetes mellitus.

The scales are shown in **Annex 1 and 2**

Glycemic variability (GV) is another secondary outcome measure. The GV will be calculated in all subjects through the use of a glucose monitor (GM) data classification scale. Subjects will be considered to have appropriate GV if their blood glucose level is in the range of 80 mg/dL – 180 mg/dL (Group C).

The GV classification is as follows:

Group A: < 50 mg/dl.

Group B: 50 – 79 mg/dl

Group C: 80 – 180 mg/dl

Group D: 181 – 350 mg/dl

Group E: > 350 mg/dl

Safety is the last secondary outcome measure. The safety measured that will be compared in both groups include death, risk of life threatening event (i.e., severe hypoglycemia associated with seizure or altered mental status), hospitalization for diabetes complication (diabetic ketoacidosis or hypoglycemia), and risk of disability or permanent damage.

E. STATISTICAL CONSIDERATIONS

Randomization

Randomization will be performed by study statistician using random-permuted blocks of size 2 and 4. Randomization assignments will be placed in sealed, opaque envelopes to be stored. Study investigators will not be blinded to treatment assignment.

Sample Size

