A goal of 20 patients is necessary for this study, but we will reach up to 40 participants in case there is any withdraw after consented and randomized. While the overall goal of the study is to demonstrate feasibility of a subsequent randomized controlled trial, limited efficacy testing will be performed. Given a sample size of 20 participants (10/grp), we will have greater than 90% power to detect a minimum standardized mean difference of 1.25 (i.e., approximately a 1.25 standard deviation difference) between groups. Effect sizes will be calculated for all study measures of interest and be used in future power calculations. On average, there are ~25 new type I/II diabetics diagnosed at Egleston hospital each month. Assuming an eligibility rate of 40%, 10 patients would be eligible to participate each month. Based on this, we are confident in our capacity to recruit 20 to 40 participants during the study period with the goal of having 20 participants to complete the study.

Statistical Analysis

Demographic characteristics will be summarized for both groups using means and standard deviations, medians and quartiles, or counts and percentages, as appropriate based on distribution. T-tests, Wilcoxon rank sums, and/or Chi squared tests will be used to assess differences between the two groups.

Primary Aims: Measures of feasibility (consent, retention, engagement, satisfaction, etc.), will be summarized overall and by group, when applicable.

Secondary Aim 1: Parental stress scale

The parental stress scale will be scored per the instrument's instructions. The total scores for the treatment groups will be compared in a cross-sectional fashion using t-tests or Wilcoxon rank sums tests as appropriate based on the distribution of scores. Changes in parental distress over-time will be evaluated using two-way repeated measures analysis of variance models. Models will include the main effect of treatment assignment, time (baseline, 1 month, 4 months), and the treatment X time interaction. The interaction term will serve as the primary statistical test for aim 2. Summary statistics, statistical significance, and effect sizes will be reported by group at each time point of interest, when applicable.

Secondary Aim 2: Glycemic variability

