Glycemic variability will be examined both as a continuous variable and a categorical variable using the ranges defined in section D. Time series analysis will be used to examine daily measures of blood glucose (obtained from patient diary's) during the study period. Variability will be measured as the probability of acute change (PAC), using methods described by Jahnig et al. (2008). Acute changes will be adjusted for time between readings. In addition, first-order autocorrelations and/or mean-square successive difference will be used to examine variation in readings as described by Jahnig. Multilevel modeling will be used to test between-group differences in variability.

Secondary Aim 3: Safety

Adverse event of interest and serious adverse events (see section D) will be summarized overall and by treatment group. For participants experiencing more than 1 episode of a specific event (e.g., severe hypoglycemia), the maximum grade and severity will be recorded. Chi-square tests will be used to compare the frequency of events between the two cohorts.

Given the exploratory nature of these secondary outcomes, we will calculate effect sizes based on the adjusted means and standard deviations or differences in proportions, when appropriate.

All analyses will be conducted using SAS v9.4 (Cary, NC).

F. ANTICIPATED RESULTS

This research will be feasible to develop a successful larger clinical trial. Due to the fixed regimen seeming to be less complicated, because there are less calculations to make than in those using the ICR group, we anticipate that parental anxiety will be decreased in the FIXED group. This will encourage more blood glucose monitoring and treatment compliance. Therefore, we anticipate GV to be decreased for the FIXED group.

G. LIMITATIONS

The major limitations of this study are related to caregiver's self-completion questionnaire and ability to contact study personnel frequently during the study period in order to report blood glucose levels and implement the insulin adjustments. More than likely, multiple insulin regimens should work, but the idea behind this study is that the fixed regimen may be easier to implement.

[figure not shown]

Figure 2: Proposed protocol.

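### Caregiver stress at 1 and 4 months is compared without adjustment for the baseline score already collected, which costs precision in the by-visit differences and effect sizes

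*Combined protocol and SAP*

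**What the plan says.** Section 5.A, Specific Aims 2(a), asks whether FIXED caregivers "experience less anxiety than the caregivers of those using an ICR with variable carbohydrate intake regimen (ICR group) at 1- and 4-months post-randomization". This is a between-arm question at two named visits.

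Section 5.D, Secondary Outcomes Measures, measures it with the PSS: "The caregiver will fill out the questionnaire at initial enrollment (prior to hospital discharge) and at each clinic follow-up throughout the study". A baseline score therefore exists for each caregiver.

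Section 5.E, Secondary Aim 1, plans two analyses:

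- By visit: "The total scores for the treatment groups will be compared in a cross-sectional fashion using t-tests or Wilcoxon rank sums tests".
- Over time: a repeated-measures analysis of variance with treatment, time (baseline, 1 month, 4 months) and their interaction. On this it states: "The interaction term will serve as the primary statistical test for aim 2".

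On reporting: "Summary statistics, statistical significance, and effect sizes will be reported by group at each time point of interest, when applicable". Section 5.E, Sample Size, adds: "Effect sizes will be calculated for all study measures of interest and be used in future power calculations". The end of the Statistical Analysis text says of the secondary outcomes that "we will calculate effect sizes based on the adjusted means and standard deviations", without saying what the means are adjusted for or which SD is meant.

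**The concern.** The question and the designated test are not the same quantity. The interaction asks whether the arms' profiles across three time points differ. It gives no estimate, with an interval, of how far apart the arms are at 1 month or at 4 months. The analyses that do speak to each visit are cross-sectional and are not said to use the baseline score.

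With as few as 10 per arm, a baseline measure of the same scale can be the most useful covariate available. Leaving it out widens the interval around each by-visit difference whenever baseline and follow-up are appreciably correlated. The pilot's effect sizes are meant to feed later power calculations, so the precision lost here is lost in a planned deliverable. No feasibility criterion in Section 5.D depends on the PSS.

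**Working it through.** **Inputs from the plan.** Two arms; three time levels; 10 per arm (Section 5.E, Sample Size), or up to 20 per arm (Section 5.B); a standardized difference of 1.25 (Section 5.E, Sample Size).

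**Assumptions, not in the plan.** Two-sided 0.05; equal SDs, set to 1; the same correlation r between any two visits, taken as 0.3, 0.5 or 0.7.

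**The plan's own figure.** Section 5.E states more than 90% power for 1.25 SD with 10 per arm. A two-sample t-test with 18 df and noncentrality 1.25 × √(10/2) = 2.80 has power 0.75. The plan names no alpha, sidedness or test for its figure. That discrepancy is a separate matter, and nothing below rests on it.

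**Degrees of freedom of the designated test.** (2 − 1)(3 − 1) = 2.

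**Unadjusted by-visit difference, 10 per arm.** SE = √(2/10) = 0.447 SD. Half-width = t(18) × SE = 2.101 × 0.447 = 0.94 SD. Power for 1.25 SD = 0.75.

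**Baseline-adjusted by-visit difference, 10 per arm.** Residual variance is 1 − r², with 2n − 3 = 17 df. The average cost of estimating the baseline slope is a factor 1 + 1/(2n − 4) = 1.0625. So SE = √((1 − r²) × 0.2 × 1.0625), half-width = t(17) × SE with t(17) = 2.110, and noncentrality = 1.25/SE.

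**Interaction, 10 per arm, 1.25 SD at both follow-ups.** The arm differences are (0, 1.25, 1.25), with mean 0.833 and sum of squared deviations 1.042. Noncentrality = (10/2) × 1.042/(1 − r), with 2 and 36 df. An effect at one follow-up only, (0, 0, 1.25), has the same sum of squares and so the same power.

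| | r = 0.3 | r = 0.5 | r = 0.7 |
|---|---|---|---|
| Unadjusted half-width (SD) | 0.94 | 0.94 | 0.94 |
| Adjusted SE (SD) | 0.440 | 0.399 | 0.329 |
| Adjusted half-width (SD) | 0.93 | 0.84 | 0.69 |
| Unadjusted power at one visit | 0.75 | 0.75 | 0.75 |
| Adjusted power at one visit | 0.76 | 0.84 | 0.95 |
| Interaction noncentrality | 7.44 | 10.42 | 17.36 |
| Interaction power | 0.64 | 0.80 | 0.96 |

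Without adjustment, matching the adjusted half-width would take 11, 13 or 18 per arm instead of 10.

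**At 20 per arm.** The half-width is 0.64 SD unadjusted against 0.62, 0.56 or 0.46 SD adjusted.

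**Scale of the score.** The English form has 18 items (total 18 to 90). The Spanish form drops English item 16 and has 17 items scored 1 to 5, so its total runs from 17 × 1 = 17 to 17 × 5 = 85. A difference in raw points does not mean the same on both forms.

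**The case against.** The strongest reply is that the designated test already uses the baseline score, as a time level, and is valid. This stands. Against that test, by-visit adjustment brings no consistent power gain: it is ahead at r = 0.3 (0.76 against 0.64), slightly ahead at 0.5 (0.84 against 0.80) and level or just behind at 0.7 (0.95 against 0.96). The comparison that favours adjustment is with the cross-sectional tests.

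A reader might also infer more than the documents support:

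- *That Aim 2a is left untested because the interaction has no direction.* Two-sided by-visit tests also reject in either direction, and the plan reports results by group at each time point, so sign and visit would be visible.
- *That chance baseline imbalance is a further harm.* At 10 per arm it exceeds 0.5 SD in about 26% of trials. The unadjusted difference is still unbiased under randomization, and this variation is already inside the 0.94 SD half-width.
- *That the undefined SD will mis-size the next trial.* That would require dividing by a residual SD and then using an unadjusted formula for an unadjusted trial. The plan proposes neither. Model-based means are a natural, though unstated, reading of the adjusted means.
- *That the annex plans a before/after analysis.* That text is generic scoring guidance for the scale, not this trial's analysis plan.
- *That baseline PSS may follow allocation.* The questionnaire is placed at enrollment, and it is enrolled participants who are randomized, so the intended order is implied though not stated.

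**Conclusion.** The point holds as a gap in estimation and precision. The plan names no baseline-adjusted FIXED minus ICR difference at 1 or 4 months, and the by-visit comparisons it does name leave out a covariate that is already collected. At 10 per arm, adjustment shortens the 95% CI half-width from 0.94 SD to 0.93, 0.84 or 0.69 SD, and raises power for 1.25 SD at one visit from 0.75 to 0.76, 0.84 or 0.95, at assumed correlations of 0.3, 0.5 and 0.7. The gain is negligible at 0.3 and material from 0.5 upward; the documents give no correlation.

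The planned tests are not invalid, and the designated interaction need not be dropped. The PSS is secondary and exploratory, so the consequence is limited to the by-visit results and the effect sizes carried forward. The change is still worth making because it costs almost nothing.

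**What to change.** In Section 5.E, Secondary Aim 1:

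- Replace the unadjusted by-visit comparisons with the FIXED minus ICR difference at 1 month and at 4 months, each adjusted for baseline PSS. Use ANCOVA by visit, or a mixed model of the two follow-up scores with treatment, visit, treatment-by-visit, baseline and baseline-by-visit. Give each difference a 95% CI and label it exploratory.
- Keep the interaction as a test of change in profile.
- Keep a rank-based version, for example rank ANCOVA, for skewed scores.
- Before pooling languages, put the totals on a common scale, for example the mean item score or the 17 shared items.
- For future power calculations, carry forward the adjusted difference, the raw follow-up SD and the baseline-to-follow-up correlation. Define the adjusted means accordingly and say which SD standardizes any effect size.

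As a clarification in Section 5.E, Randomization, which says "Randomization assignments will be placed in sealed, opaque envelopes to be stored", add that baseline PSS is completed before the envelope is opened.

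**Cost.** Wording only: no new data or visits, and the models are standard in SAS v9.4. Adjustment uses 1 df and gains little if the correlation is near 0.3. Two by-visit results give, by simulation under no effect, a 0.09 to 0.10 chance that at least one is significant, similar to the 0.08 to 0.10 for the tests already planned. The exploratory label covers this; Holm would bring it to about 0.05 at some cost in power.

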The plan is to enroll from 20 to 40 children and adolescent subjects with newly-diagnosed T1DM. Twenty will be randomized to the FIXED group and twenty will be randomized to the ICR group. The subjects will be selected from children and adolescents admitted to CHOA-Egleston with a diagnosis of new-onset Diabetes Mellitus. Participation in this study will be determined by a set of inclusion/exclusion criteria.

1) Inclusion Criteria

For enrollment in the study, subjects must: (1) Have Confirmed diagnosis of T1DM based on the most recent ADA criteria [16]; (2) Be 8 - 14 years of age; (3) Begin monitoring with a glucose monitor prior to discharge from the hospital; and (4) Have the ability to understand and be willing to adhere to the study protocol. (5) English or Spanish speakers.

2) Exclusion criteria

For enrollment in the study, subjects may not: (1) Have a clinically significant major organ system disease (i.e., hypertension, hyperlipidemia, or obesity); (2) Be on glucocorticoid therapy; (3) Have Type 2 Diabetes Mellitus; (4) Have Polycystic Ovarian Syndrome (PCOS); (5) Have a BMI > 85th %ile; (6) Have Acanthosis Nigricans; (7) Have any form of renal impairment; (8) Have Cystic Fibrosis; (9) Have Glucocorticoid-, Chemotherapeutic-, or any other Medication-induced form of Diabetes; (10) Be using any basal insulin other than Glargine insulin; (11) Have cognitive impairment (> 2 grades behind age-appropriate grade in school); (12) Be in Foster Care; (13) Have any history of DFCS involvement; and (14) If female, be pregnant or breast-feeding.

C. DATA MANAGEMENT

All data, including patient demographics, history, and laboratory tests will be collected on standardized forms and entered into an electronic database, REDCap. REDCap is a HIPPA-compliant, web-based, data capturing tool used in over 130 countries. Features include user-specific credentials, data-logging, longitudinal data modeling and more. Enrolled patients will be assigned a study ID. Subjects will only be identified in REDCap by their study ID. The patient's name, MRN and study ID will be kept in a secure file in a double lock in a filing cabinet under [name] supervision in the Emory Children's Center. Records will be maintained for 10 years as required for IRB studies.

D. OUTCOME MEASURES

1) Primary Outcome Measures

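### The stated power of more than 90% for a 1.25 SD difference with 10 per group does not hold for a two-group t-test (about 75%), and holds for the designated treatment-by-time interaction test only if the within-caregiver correlation is high

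*Combined protocol and SAP*

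**What the plan says.** The Sample Size paragraph of section 5.E contains the only power statement in the document. It is tied to 10 per group ("Given a sample size of 20 participants (10/grp") and claims that "we will have greater than 90% power to detect a minimum standardized mean difference of 1.25". It names no outcome, test, significance level or sidedness.

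The Statistical Analysis text for the parental stress scale, headed Secondary Aim 1 (Specific Aim 2a in section 5.A), plans two kinds of comparison. Total scores are to be "compared in a cross-sectional fashion using t-tests or Wilcoxon rank sums tests as appropriate based on the distribution of scores". In addition, "Changes in parental distress over-time will be evaluated using two-way repeated measures analysis of variance models". On the model terms it says: "Models will include the main effect of treatment assignment, time (baseline, 1 month, 4 months), and the treatment X time interaction". It then settles which result decides: "The interaction term will serve as the primary statistical test for aim 2".

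The plan gives no correlation between a caregiver's repeated scores, no expected pattern of the group difference over time, and no power for the interaction. On numbers, the Study Population section says "Twenty will be randomized to the FIXED group and twenty will be randomized to the ICR group", while the Sample Size paragraph aims for 20 completers in total and treats enrolment up to 40 as cover for withdrawals.

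**The concern.** A standardized mean difference between two groups is the effect measure of a single cross-sectional comparison. The test that the plan designates is an interaction over three time points, with (2 − 1)(3 − 1) = 2 degrees of freedom. Its power also depends on how the group difference changes over time and on rho. So there are two questions: is the printed figure right for the comparison that it describes, and does it carry over to the designated test?

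At stake is the accuracy of a claim that the plan chose to print. Readers of the stress results will have only that figure to judge what the pilot could detect. Anyone sizing the later trial on the same interaction would need a value for rho, and the plan does not say that it will report one.

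**Working it through.** **Inputs from section 5.E.** n = 10 per group; difference 1.25 SD; three time points (baseline, 1 month, 4 months).

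**Assumptions not in the documents.** Two-sided alpha 0.05, equal SDs, complete data, no baseline difference, compound symmetry with correlation rho (shown as a range), and two effect patterns.

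**1. The plan's own figure (two-sample t-test, 10 per group).** Noncentrality = 1.25 × √(10/2) = 2.795, with 18 df.

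| Alpha | Power, t | Power, normal approximation |
|---|---|---|
| two-sided 0.05 | 75.3% | 79.8% |
| one-sided 0.05 (= two-sided 0.10) | 85.1% | 87.5% |
| one-sided 0.10 | 92.6% | 93.5% |

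Of these settings, only one-sided 0.10 exceeds 90%, and the plan does not state it. At two-sided 0.05, 90% power with 10 per group needs a difference of about 1.53 SD. For 1.25 SD, 15 per group is the smallest size above 90% (91.1%), and 20 per group gives 97.1%.

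**2. The designated test (interaction F-test).** Power comes from the noncentral F with 2 and 2(2n − 2) = 36 df, where

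lambda = (n/2) × Σ(δ_t − mean δ)² / (1 − rho).

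- Step pattern (0, 1.25, 1.25): mean 0.833; sum of squares 0.694 + 0.174 + 0.174 = 1.042; lambda = 5 × 1.042/(1 − rho) = 5.21/(1 − rho).
- Gradual pattern (0, 0.625, 1.25): mean 0.625; sum of squares 0.391 + 0 + 0.391 = 0.781; lambda = 5 × 0.781/(1 − rho) = 3.91/(1 − rho).

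| rho | lambda, step | Power, step | lambda, gradual | Power, gradual |
|---|---|---|---|---|
| 0.3 | 7.44 | 64.5% | 5.58 | 51.5% |
| 0.5 | 10.42 | 79.7% | 7.81 | 66.7% |
| 0.7 | 17.36 | 95.6% | 13.02 | 88.2% |

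Power reaches 90% at rho of about 0.62 (step) or 0.72 (gradual). Simulation agrees: 64.5%, 79.6% and 95.8% for the step pattern, and 51.6%, 66.5% and 88.3% for the gradual one.

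**3. Interaction against t-test.** The interaction passes the t-test's 75.3% at rho of about 0.45 (step) or just under 0.6 (gradual). Below that it is weaker, and above it is stronger.

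**4. Sensitivity to the covariance assumption (10 per group).** Under an AR(1) correlation of 0.5, simulated power is 71% (step) and 56% (gradual). The multivariate form of the test (2 and 17 df, compound symmetry) gives 60%, 75.5% and 93.5% for the step pattern at rho 0.3, 0.5 and 0.7.

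**5. If 20 per group complete.** Interaction power at rho 0.3 and 0.5 is 93% and 99% (step), or 84% and 94% (gradual). Power reaches 90% at rho of about 0.21 (step) or 0.41 (gradual).

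**The case against.** The strongest reply is that this is a feasibility pilot. The numerical success thresholds in section 5.D all concern feasibility, efficacy testing is described as limited, and the secondary outcomes are called exploratory. No decision rule rests on the interaction p-value. That stands, and it keeps the point minor. It does not make the printed figure right, and the plan did attach a power claim and name a deciding test.

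A second reply is that up to 40 may enrol. That stands in part: with 20 completers per group the two-group figure holds (97.1%), and the interaction falls short only at low correlations. But the claim is written for 10 per group, and 20 completers in total is the stated goal.

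Three stronger readings are tempting, and the documents do not support them.

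- A reader might infer that designating the interaction is what costs the power. It is not: the t-test itself falls short of 90%, and at moderate to high rho the interaction is the more powerful of the two.
- A reader might infer that the interaction would miss a 1.25 SD effect in one in five to one in two trials. Those rates belong to rho between 0.3 and 0.5. At rho 0.7 the miss rate is about 4% (step) or 12% (gradual), and the documents do not favour any value of rho.
- A reader might infer that a non-significant interaction will be taken as evidence against a 1.25 SD effect. The plan does not say so. It says that effect sizes will feed later power calculations.

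**Conclusion.** The power statement is wrong as written for 10 per group. At two-sided 0.05 the two-group comparison has about 75% power, not more than 90%. The designated interaction reaches 90% only if rho exceeds about 0.62 (difference present at both visits) or 0.72 (difference building up), and the plan states neither rho nor the pattern.

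The t-test result rests on the assumed alpha. The interaction results rest also on compound symmetry, complete data and no baseline difference, and they move by several percentage points or more under other covariance structures. The conclusion is that the stated power is not delivered at the stated size. It is not that the interaction is a poor choice of test. Severity is minor.

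**What to change.** In Sample Size:

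1. Correct the two-group figure; do not merely relabel it. Either give about 75% power for 1.25 SD with 10 per group (two-sided 0.05), or give about 1.53 SD as the difference detectable with 90% power. Say that this applies to the cross-sectional comparisons at each visit. If another alpha was intended, state it.
2. Add the power of the designated test. For example: with 10 completers per group, two-sided alpha 0.05, compound symmetry, complete data and no baseline difference, the 2-df treatment-by-time interaction has about 64%, 80% and 96% power for a 1.25 SD difference at both 1 and 4 months if rho is 0.3, 0.5 or 0.7, and about 51%, 67% and 88% if the difference is 0.625 SD at 1 month and 1.25 SD at 4 months. Note that power is higher if 20 per group complete (93% and 99% at rho 0.3 and 0.5 for the first pattern).
3. Optionally, report the observed within-caregiver correlation with its confidence interval. The interval will be wide: with 20 caregivers, an observed 0.5 has a 95% interval of about 0.07 to 0.77. It can inform a range for the later trial but cannot fix a value.

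The cost is a few sentences and at most one extra reported estimate, with no added patients, visits or data. The downside is a less favourable power figure that depends on stated assumptions.
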